#### Feeling warm or hot

The radiowaves used in MRI are like those your cellphone uses, but much stronger. Sometimes they are strong enough to make you feel warm (just like standing in bright sunshine makes you feel warm). MRI scanners are designed to try to avoid you getting too hot. However, if you start to feel uncomfortable, squeeze the emergency ball and tell the technologist.

#### Peripheral nerve stimulation (tingling or twitching)

The magnetic field inside the scanner changes very quickly while the scanner is running. If it changes too quickly, it can give you tingling sensations or make you twitch. MRI scanners are designed to try to avoid this. However, if you experience tingling or twitching, squeeze the emergency ball and tell the technologist.

#### Claustrophobia (discomfort in enclosed spaces)

Some people get panic attacks inside enclosed spaces. This is called 'claustrophobia', which means 'fear of confined spaces'. If you know that you are claustrophobic, tell study personnel before your scan. Some people only find out they are claustrophobic when they have an MRI for the first time. If you feel anxious or panicky inside the scanner, squeeze the emergency ball and the technologist will get you out.

#### Quench

In very rare circumstances, the scanner can lose its magnetic field. This happens very suddenly and is known as a 'quench'. The helium that helps keep the magnetic field strong will then escape from the scanner. The scanner is connected to a vent so that the helium will go outside the building. However, if for some reason the vent doesn't work properly, helium might fill the scan room, making it difficult to breathe. In the very unlikely event of a quench, the technologists will get you out of the scanner immediately.

#### Gadolinium contrast (MRI dye)

You might need to have an injection of gadolinium contrast (a dye that lights up on the images). Sometimes the dye can cause side effects like headache, dizziness, or nausea (feeling slightly sick) for a short time after the injection. Some people might get an itchy skin rash, although this is uncommon (about 1 in 1000 people). It is also possible to have a serious allergic reaction called 'anaphylactic shock', which can cause swelling of the mouth and make it difficult to breathe. However, this is very rare (about 1 in 10,000 people). The technologist will tell you ahead of time when the dye is about to be injected, and will keep in contact with you to make sure that you're OK. If you feel any discomfort, squeeze the emergency ball and the technologist will come into the room to check on you.

The dye leaves your body in your pee. Provided your kidneys are healthy, it should be almost all gone in about 24 hours. However, if you have kidney problems, you should tell study personnel before your scan. In rare situations, people with severe kidney problems have developed a serious condition called 'nephrogenic systemic fibrosis' from certain types of dye.

Fairly recently (in 2014) scientists discovered that if people get many injections of certain types of dye, some of the dye seems to stay in their brain for a long time afterwards. Doctors don't know yet whether this is bad for you or not. However, if you have already had dye many times before, you should tell study personnel before your scan.

#### CT Scan risks (if unable to undergo MRI):

Version: 11.0

Radiation Exposure: During this study, you will have exposure to radiation from liver CT scans if you are unable to undergo MRI, as well as CT-guided biopsy. This radiation exposure is not necessary for your medical care and is for research purposes only. This means that you will be exposed to small doses or amounts of radiation. The risk from this amount of radiation is less than the risk from everyday exposure to the sun. The risks of receiving very small doses of radiation are thought to be low. These risks are not actually known.

Pregnant women cannot be exposed to radiation. Women must have a negative pregnancy test before they can have a CT scan.

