#### 7.2 Laboratory Procedures/Evaluations

#### 7.2.1 Clinical Laboratory Evaluations

#### Screening Laboratory Tests

- **Hematology:** hemoglobin, hematocrit, white blood cells (WBC) with differential count, platelet count.
- **Biochemistry:** creatinine, total bilirubin, alanine aminotransferase (ALT), aspartate aminotransferase (AST), albumin, alkaline phosphatase, sodium, glucose
- Coagulation: Prothrombin Time (International Normalized Ratio/INR)
- Tumor Marker: alpha fetoprotein (AFP)
- **Pregnancy test**, usually to be done within 24 hours prior to study intervention and results must be available prior to administration of study product.

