#### 7.3 Study Schedule

#### 7.3.1 Screening

#### Screening Visit (Day -20 to -1)

- Obtain informed consent of potential participant verified by signature on written informed consent for screening form.
- Review medical history to determine eligibility based on inclusion/exclusion criteria.
- Review medications history to determine eligibility based on inclusion/exclusion criteria.
- Perform medical examinations needed to determine eligibility based on inclusion/exclusion criteria.
- Collect blood for hematology, biochemistry, coagulation (Section 7.2.1), AFP, IL-8 levels.
- MRI abdomen (or CT if not eligible), 3 phase IV contrast, liver protocol.
- CT chest (with or without IV contrast).
- Ultrasound or CT guided core tumor biopsy.
- Schedule study visits for participants who are eligible and available for the duration of the study.
- Provide participants with instructions needed to prepare for first study visit.
- Randomize participant to either Arm 1 or Arm 2 of study treatment (see Study Schema).

Version: 11.0

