#### 7.3.2 Enrollment/Baseline

#### **Enrollment/Baseline Visit (Visit 1, Day 1, Cycle 1)**

- Verify inclusion/exclusion criteria.
- Record vital signs, results of physical examinations, and medical history.
- Collect blood for hematology, biochemistry, coagulation, and pregnancy test (Section 7.2.1).
- Administer the study treatment (Arm 1 (control) Nivolumab 240mg IV every 2 weeks monotherapy; Arm 2 Nivolumab 240 mg IV plus BMS-986253 2400mg every 2 weeks...
- Observe for infusion reactions and treat if needed (see Package Insert for Nivolumab and Investigator Brochures for BMS-986253).

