#### Visit 5, Cycle 3 (Day 59 +/- 3)

- Record adverse events as reported by participant or observed by investigator.
- Record vital signs, results of medical history, physical exam, height/weight, performance status (ECOG).
- Collect blood for hematology, biochemistry, coagulation (Section 7.2.1). AFP to be determined every 8 weeks for 12 months then every 12 weeks thereafter

Version: 11.0

- Collect blood for IL-8 level (Cycle 3 only)
- Administer the study treatment (Arm 1 (control) Nivolumab 240mg IV every 2 weeks monotherapy; Arm 2 Nivolumab 240 mg IV plus BMS-986253 2400 mg IV every 2 weeks.
- MRI abdomen (or CT if not eligible), 3 phase IV contrast, liver protocol. To be performed every 8 weeks for 12 months, then every 12 weeks thereafter
- CT chest (with or without IV contrast). To be performed every 8 weeks for 12 months, then every 12 weeks thereafter
- Tumor objective response determination (RECIST v. 1.1). To be performed every 8 weeks for 12 months, then every 12 weeks thereafter
- Ultrasound or CT guided core tumor biopsy (Cycle 3 only).

#### 7.3.3.5 Visit 6

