# 20 Schedule of Events

STUDY DAY	Prestudy, screening  (Day -20 to -1)	C1D1	(+/- 3 days)	C2D1 (Day 29+/- 3 days)	C2D15 (Day 45+/- 3 days)	C3D1 (Day 59+/- 3 days)	C3D15 (Day 74+/- 3 days)	Subsequent Visits* (Estimate 24 visits average)	Follow Up F
Study Team Procedures									
Informed Consent	Х								
Medical History	Х		Х	Х	Х	Х	Х	Х	Х
Physical Exam	Χ		Х	Х	Х	Х	Х	X	Х
Vital Signs	Х		Х						Х
Weight	Х		Х	Х	Х	Х	X	Х	Х
Height	Х								Х
ECOG Performance Status	Х		X	X	Х	X	Х	X	Х
Toxicity Evaluations (AE reporting)		Х	Х	Х	Х	Х	Х	Х	Х
Concomitant Medications	Х	Х	X	Х	Х	Х	Х	Х	Х
RECIST v. 1.1 A	Х					Х		Х	X F
Study Drugs B		Х	Х	Х	Х	Х	Х	Х	
Venipuncture	Х	Х	Х	Х	Х	Χ	Х	Х	
Laboratory Assessments									
CBC, CMP, INR	Х	Х	Х	Х	Х	Х	Х	Х	Х

Version: 11.0

AFP C	Х					Х		Х	X F
TSH Testing	Х	X		X		X		X	
Venipuncture	Х	Х	Х	Х	Х	Х	X	X	Х
Serum Pregnancy Test		Х							
Translational Peripheral Blood Sample D	X					X			
Tumor Biopsy	Х					Х			
Fresh frozen tissue from core biopsy (Processing)	X					Х			
Imaging Assessments									
Imaging E	Х					Х		Х	X F

A every 8 weeks for 12 months, see Schema

B Arm 1: Nivolumab 240 mg IV every 2 weeks; Arm 2: BMS-986253 2400mg IV + Nivolumab 240mg IV every 2 weeks; C AFP to be checked pre-study and at every 8 weeks for 12 months, see Schema IL-8 level and other, cycle 3 only E 3-phase liver CT, or MR abdomen with contrast every 8 weeks for 12 months, see Schema

F every 3 months for 1 year, See Schema
\*Scheduled treatment visits occurring after Cycle3

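### The protocol requires a negative pregnancy test before CT, but the screening visit lists CT with no test, and the visit lists and Schedule of Events place the test only at C1D1

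*Combined protocol and SAP*

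**What the plan says.** **The rule.** Under the CT scan risks in Section 2.4.1.2, the protocol says "Pregnant women cannot be exposed to radiation" and then "Women must have a negative pregnancy test before they can have a CT scan". That part is headed as applying to participants who cannot have MRI. It names liver CT and CT-guided biopsy as the sources of exposure and describes the exposure as being for research only.

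**Screening.** Section 7.3.1, "Screening Visit (Day -20 to -1"), lists "CT chest (with or without IV contrast") with no condition attached. It also lists abdominal MRI, or CT if MRI cannot be done, and an ultrasound- or CT-guided core biopsy. The bloods are hematology, biochemistry, coagulation, AFP and IL-8. Randomisation is the last item.

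**The test.** Section 7.3.2 (Visit 1, Day 1, Cycle 1) has "Collect blood for hematology, biochemistry, coagulation, and pregnancy test (Section 7.2.1"). In the Schedule of Events (Section 20), the row "Serum Pregnancy Test" is marked under C1D1 and nowhere else. Section 7.2.1 lists the test under screening laboratory tests, with the timing "usually to be done within 24 hours prior to study intervention and results must be available prior to administration of study product". Inclusion criterion 9 asks for a blood test in the 24 hours before study treatment starts.

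**Repeat scans.** Section 7.3.3.4 (Visit 5) has "CT chest (with or without IV contrast). To be performed every 8 weeks for 12 months, then every 12 weeks thereafter". Section 7.3.7 lists chest CT again at follow-up. Neither list includes a pregnancy test.

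**The concern.** The protocol sets a protective condition for CT, but its operational sections do not carry that condition out. Coordinators usually work from the visit lists and the Schedule of Events. A site that follows those two exactly would perform the screening CT with no pregnancy result available, and the risk text would be met only if someone remembered to add an unscheduled test.

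What is at stake is participant safety and protocol compliance; power and the ORR comparison are not affected. There is one small consequence for the analysis. Randomisation falls within screening and Section 10.3 analyses all randomised participants. A woman whose pregnancy is first found at C1D1 would therefore stay in the analysis set untreated, and one such case is 1/25 = 4% of an arm.

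**Working it through.** The plan gives no figure to reproduce, so the check is a comparison of sections in time order.

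| Place | CT exposure listed | Pregnancy test |
|---|---|---|
| 2.4.1.2, CT risks | Liver CT if no MRI; CT-guided biopsy | Negative result required before a CT scan |
| 7.3.1, Day -20 to -1 | Chest CT for all; liver CT if no MRI; biopsy by ultrasound or CT | None |
| 7.2.1, screening laboratory tests | Not applicable | Listed; usually within 24 hours before study intervention |
| 5.1, inclusion 9 | Not applicable | Within 24 hours before study treatment |
| 7.3.2, Day 1 | None | Listed |
| 7.3.3.4 and 7.3.7 | Chest CT for all; liver CT if no MRI | None |
| 20, Schedule of Events | Imaging at screening, C3D1, later visits and follow-up | C1D1 only |

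**Step 1: order of events.** Counting no Day 0, a CT on Day -20 comes 20 days before a Day 1 test, and a CT on Day -1 comes 1 day before it. As scheduled, the CT precedes the test by about 1 to 20 days. If a site draws the test at the start of the 24-hour window, the result could precede only a CT done within the last day or so of screening.

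**Step 2: does Section 7.2.1 close the gap?** Its heading points to screening, but its timing is tied to the study intervention and its deadline to administration of study product. Nothing links it to imaging. The blood item in 7.3.1 cites Section 7.2.1, but only for hematology, biochemistry and coagulation.

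**Step 3: does the scope of the rule matter?** If the rule covers any CT, it covers the chest CT that every participant has at screening. If it covers only the exposures named in 2.4.1.2, it still covers liver CT and CT-guided biopsy, and both can occur at screening before the scheduled test. The mismatch exists on either reading; only the number of women affected changes.

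**Step 4: later scans.** Imaging every 8 weeks over 52 weeks gives 52/8 = 6.5, so 6 scans (weeks 8, 16, 24, 32, 40 and 48). With screening, 1 + 6 = 7 chest CTs in the first year for a participant imaged for the full 12 months. One scheduled test accompanies them, and it follows the first scan. The risk text does not say whether a test is needed before each scan, so this is a question of scope and not a demonstrated breach.

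**The case against.** The strongest reply concerns scope. The CT risk text is limited by its heading to participants who cannot have MRI, names only liver CT and CT-guided biopsy, and describes research exposure. Section 7.1.2 lists chest CT as standard of care. The rule may therefore never have been meant for the chest CT. That reading is fair, and it is why the scope needs to be stated. It does not remove the mismatch (step 3). Nor does the standard-of-care label settle it: Section 7.1.2 gives that label to the liver CT as well, and Section 7.2.2 gives it to the pre-treatment biopsy, yet the CT risk text names both kinds of procedure.

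A reader might infer several stronger claims that the documents do not support:

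- **That every woman of childbearing potential is scanned in breach of the rule.** The risk text is itself protocol text. A site can comply by adding a test, and nothing in Section 7.3.1 or the Schedule forbids that. Exposure could occur; it is not certain.
- **That no test could properly take place before C1D1.** Section 7.2.1 puts the test under a screening heading, and its timing is only the usual one.
- **That pregnancy cannot be detected as an exclusion until after CT and randomisation.** Section 7.3.1 requires history review and examination against the eligibility criteria, so a known pregnancy can be found at screening. Sections 5.6.1 and 5.6.3 also require documentation of each criterion before enrolment is confirmed. Those checks do not bring the test ahead of the scans, because screening imaging itself supplies evidence of measurable disease. What remains exposed is an unrecognised pregnancy.
- **That a test is required before every repeat scan.** The text does not say so. Pregnancy on treatment is partly addressed by the contraception requirement in inclusion criterion 10 and by Section 8.4.4.

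Finally, Section 7.2.4 says specimen analysis was complete as of February 2024 and no more samples will be collected. This suggests that screening may be over, but does not establish it. If it is over, a change to the screening column has little practical reach; the on-treatment and follow-up scans would still need an answer.

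**Conclusion.** The inconsistency stands. The protocol makes a negative pregnancy test a condition for CT, while the screening visit list and the Schedule of Events put CT first and the test at C1D1. A site following the schedule could expose a woman with an unrecognised pregnancy to CT, and randomise her, before she is tested.

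The size cannot be given as a head count. The documents do not say how many women of childbearing potential are expected among the 50 to be randomised, or among those screened (about 70 in Section 5.8, 90 in Section 5.5). On the wide reading, all such women who reach screening imaging are affected; on the narrow reading, only those who have liver CT or a CT-guided biopsy. The conclusion rests on the visit lists and the Schedule being what sites follow, and on no separate instruction adding an earlier test; none appears in the documents.

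**What to change.** Reconcile Sections 2.4.1.2, 7.1.2, 7.2.1, 7.3.1, 7.3.2 and 20 in one amendment:

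1. State which CT procedures the pre-CT testing rule covers. Say explicitly whether it includes the routine chest CT and the repeat scans in Sections 7.3.3.4 and 7.3.7.
2. Make the screening visit list and the screening column of the Schedule carry out that rule, whatever it is.
3. Resolve the mismatch in Section 7.2.1 between its screening heading and its treatment-linked timing, and say how it relates to inclusion criterion 9.
4. Correct the description of CT exposure in Section 2.4.1.2 so that it includes the chest CT listed for everyone, and reconcile its research-only wording with the standard-of-care labels in Sections 7.1.2 and 7.2.2. Footnote E of the Schedule, which names liver CT or abdominal MR but not chest CT, should be aligned at the same time.

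The clinical rule, including any repeat testing, is for the sponsor to decide; this point asks only that the sections agree.

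The cost is an amendment to the text and Schedule. If the intended rule requires a result before the screening CT, it adds one assay for a subgroup whose blood is already drawn at that visit, and the draw, result and scan must then be sequenced. The documents do not cost that sequencing.

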#### 2.4.2 Known Potential Benefits

Nivolumab has been evaluated in a phase II study in HCC patients (Checkmate 040 study) and was recently FDA approved for use in HCC patients. The ORR was noted to be 15% with 3% having a CR and 12% having a PR (7). Most recent updates on this trial (N=154) have shown that the median time to response was 2.8 months. The median DOR has not been reached after 48 months of follow up. Of those patients responding, 59% had a DOR of greater than 12 months. Median OS based on best overall response (RECIST v.1.1) and stratified as complete/partial response, stable disease, and progressive disease was not reached, 16.7 months, and 8.9 months, respectively (El-Khoueiry et al, ASCO-GI, 2018).

In the phase I study of BMS-986253 in solid tumor malignancy patients (CA027-001, Investigator Brochure), there were no observed objective radiographic responses in the 15 participants. In the phase 1/2a study evaluating the combination of BMS-986253 and Nivolumab (CA027-002) in advanced cancer patients there is no efficacy data available at the present time.

It is possible that some study subjects who receive the study therapies may experience an improvement in their cancer during the study. Others with HCC may benefit in the future from what is learned in this study.

# 3 Objectives and Purpose

#### 3.1 Primary Objective

The primary objective is to determine the ORR of BMS-986253 in combination with Nivolumab in comparison to Nivolumab monotherapy using RECISTv.1.1 criteria. Additionally, the safety of the BMS-986253 in combination with Nivolumab will be determined.

#### 3.2 Secondary Objectives

The secondary objectives are to determine the TTR, DOR, PFS, and OS for subjects receiving BMS-986253 in combination with Nivolumab in comparison to Nivolumab monotherapy. An additional secondary objective is to evaluate the tumor microenvironment (TME) using novel NYU technologies of 30-parameter flow cytometry and single cell RNAseq on pre- and on-treatment fresh core tumor biopsies.

Version: 11.0

#### 4 Study Design and Endpoints

#### 4.1 Description of Study Design

The trial is a phase II, randomized controlled, single blinded study evaluating 2 study arms: Arm 1 (control) Nivolumab 240mg IV every 2 weeks monotherapy; Arm 2 Nivolumab 240 mg IV plus BMS-986253 2400 mg IV every 2 weeks(see Study Schema). Six patients will be observed for toxicity in each arm The trial will be performed at two sites. Holding of dose will occur if a dose limiting toxicity occurs on any arm.

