# **Protocol Summary**

[figure not shown]
i rotocor carrilla	,	
Title	A Phase II, Randomized, Controlled Trial of Nivolumab in Combination with BMS-986253 in Advanced Hepatocellular Carcinoma (HCC) Patients	
Short Title	Nivolumab Combined with BMS-986253 in HCC Patients	
Brief Summary	A phase II clinical trial is utilized to examine whether BMS-986253 (25 subjects) when combined with Nivolumab offers improved radiographic objective response rates (ORR) over Nivolumab monotherapy (25 subjects in advanced HCC patients. Primary endpoint, ORRs, will be assessed at 2 month increments while on treatment. Safety will be verified for the Nivolumab/BMS-986253 combination. Secondary endpoints of time to response (TTR), duration of response (DOR), progression free survival (PFS), and overall survival (OS) will also be assessed. Pre- and on-treatment tumor biopsies will be utilized for translational/correlative research.	
Phase	Phase 2	
Objectives	
 
Determine the ORR of BMS-986253 in combination with Nivolumab.
 
Determine the safety of BMS-986253 in combination with Nivolumab.
 
Determine the TTR, DOR, PFS, and OS for subjects receiving BMS-986253 in combination with Nivo.
 
Exploratory study of the tumor microenvironment (TME) using novel NYU technologies of 30-parameter flow cytometry and single cell RNAseq on pre- and on-treatment fresh core biopsies.
 
	
Methodology	Randomized, controlled, single blind trial	
Endpoint	Primary Endpoints: ORR of BMS-986253 in combination with Nivolumab in comparison to Nivolumab monotherapy and safety of BMS-986253 in combination with Nivolumab.  Secondary Endpoints: TTR, DOR, PFS, OS, and exploratory analysis of the HCC TME in subjects receiving either BMS-986253 in combination with Nivolumab in comparison to Nivolumab monotherapy	
Study Duration	The duration of this study from enrollment until completion of data analysis is up to 6 years	
Participant Duration	2-5 years	
Enrollment Period	2 years	
Duration of IP administration	2-5 years	
Population	50 total male and female participants: 25 participants Nivolumab monotherapy group, 25 participants Nivolumab/BMS-986253 combination, Age ≥ 18, Two U.S. sites	
Study Centers/Sites	Multicenter (Two): NYU Langone Health and Univ. of Pennsylvania	
Number of participants	50 participants across 2 sites	
Description of Study Agent/Procedure	Nivolumab 240 mg IV every 2 weeks + BMS-986253 2400 mg IV every 2 weeks	

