# **Schematic of Study Design**

Version: 11.0

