#### 4.2 Study Endpoints

#### 4.2.1 Primary Study Endpoints

The primary endpoint will be the ORR of the Nivolumab and BMS-986253 combination, and the ORR of the Nivolumab monotherapy. ORR will be determined based upon RECIST v. 1.1 criteria. The safety of BMS-986253 in combination with Nivolumab will be determined.

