#### 6.1.5 Dosing and Administration

Nivolumab will be administered by infusion over 30 minutes through an intravenous line containing asterile, non-pyrogenic, low protein binding in-line filter. BMS-986253 will be administered by infusion over 120 minutes through an intravenous line containing asterile, non-pyrogenic, low protein binding inline filter. If the patient's weight is < 35 kg, the infusion will be administered over 180 minutes. Pore size of 0.2 micrometer to 1.2 micrometer is acceptable for Nivolumab and BMS-986253 (see package insert and IB, respectively).Do not co-administer other drugs through the same intravenous line. Flush the intravenous line at end of infusion. When administering BMS-986253 with Nivolumab, infuse Nivolumab first followed by a 30 minute period of observation followed by infusion BMS-986253 over 120 minutes on the same day. Use separate infusion bags and filters for each infusion.

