# ADVERSE EVENT MANAGEMENT FOR NIVOLUMAB MONOTHERAPY OR FOR NIVOLUMAB IN COMBINATION WITH BMS-986253

Adverse Reaction	Severity*	Dose Modification
	Grade 2 diarrhea or colitis	Withhold dose a
Colitis	Grade 3 diarrhea or colitis	Withhold dose when single
		agent (Nivolumab
		monotherapy), Permanently
		discontinue when administered
		with additional study drug
	Grade 4 diarrhea or colitis	Permanently discontinue
Pneumonitis	Grade 2 pneumonitis	Withhold dose a
	Grade 3 or 4 pneumonitis	Permanently discontinue
	If AST/ALT is within normal	
	limits at baseline and increases	
	to more than 3 and up to 5 times	
	ULN	
Hepatitis	If AST/ALT is more than 1 and	Withhold dose b
	up to 3 times ULN at baseline	
	and increases to more than 5	
	and up to 10 times ULN	
	If AST/ALT is more than 3 and	
	up to 5 times ULN at baseline	
	and increases to more than 8	
	and up to 10 times ULN	
	If AST or ALT increase to more	Permanently discontinue
	than 10 times the ULN or total	
	bilirubin increases to more than	
	3 times the ULN	
Hypophysitis	Grade 2 or 3 hypophysitis	Withhold dose a
	Grade 4 hypophysitis	Permanently discontinue
Adrenal Insufficiency	Grade 2 adrenal insufficiency	Withhold dose a
	Grade 3 or 4 adrenal	Permanently discontinue
T 15:1 1 M 10:	insufficiency	145
Type I Diabetes Mellitus	Grade 3 hyperglycemia	Withhold dose a
	Grade 4 hyperglycemia	Permanently discontinue
Nephritis and Renal Dysfunction	Serum Cr more than 1.5 and up	Withhold dose a
	to 6 times the ULN	
	Serum Cr more than 6 times the	Permanently discontinue
	ULN	
Skin	Grade 3 rash or suspected	Withhold dose a
	Stevens-Johnson syndrome	
	(SJS) or toxic epidermal	
	necrolysis (TEN)	D " "
	Grade 4 rash or confirmed SJS	Permanently discontinue
- L PC	or TEN	Maria I I I I I
Encephalitis	New-onset moderate or severe	Withhold dose a
	neurologic signs or symptoms	

Version: 11.0

	Immune-mediated encephalitis	Permanently discontinue
	Other Grade 3 adverse reaction	Withhold dose a
	First Occurrence	
	Recurrence of same Grade 3	Permanently discontinue
	Adverse reactions	
	Life threatening or Grade 4	Permanently discontinue
	adverse reaction	
Other	Grade 3 myocarditis	Permanently discontinue
	Requirement for 10 mg per day	Permanently discontinue
	or greater prednisone or	
	equivalent for more than 12	
	weeks	
	Grade 2 or 3 adverse reactions	Permanently discontinue
	lasting 12 weeks or longer	

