#### 6.1.8 Duration of Therapy

Duration of therapy will be at least three cycles, unless AE requiring dose modification is required (6.1.7), at which point first radiographic imaging is performed. From a statistical standpoint, this will be an evaluable participant for objective response based on RECISTv1.1 criteria. One cycle is defined as 4 weeks.

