# 8.5 Reporting Procedures – Notifying the Study Supporter

The study clinician will complete a SAE Form within the following timelines:

- All deaths and immediately life-threatening events, whether related or unrelated, will be recorded
  on the SAE Form and submitted to the DSMC/study supporter within 24 hours of site awareness.
   See Section 1, Key Roles for contact information.
- Other SAEs regardless of relationship will be submitted to the DSMC/study supporter within 72 hours of site awareness.

All SAEs will be followed until satisfactory resolution or until the site investigator deems the event to be chronic or the adherence to be stable. Other supporting documentation of the event may be requested by the DSMC/study supporter and should be provided as soon as possible.

As a follow-up to the initial report, within the following 48 hours of awareness of the event, the investigator shall provide further information, as applicable, on the unanticipated event or the unanticipated problem in the form of a written narrative. This should include a copy of the completed Unanticipated Problem form, and any other diagnostic information that will assist the understanding of the event. Significant new information on ongoing unanticipated adverse effects shall be provided promptly to the study supporter.

SAEs, whether related or not related to study drug, and pregnancies must be reported to BMS within 24 hours of becoming aware of the event. SAEs must be recorded on either MedWatch, or approved site SAE form.

Pregnancies must be reported and submitted to BMS on either the MedWatch or approved site SAE form. In addition the Pregnancy Surveillance Form (3 Parts) must be completed and submitted to BMS. BMS will perform due diligence follow-up using the BMS Pregnancy Form which the investigator must complete.

SAE Email Address: [contact]

SAE [contact]

Adverse Events that are routinely collected according to GCP shall be submitted to BMS every three (3) months by the last working day of the third month.

Version: 11.0

The Adverse Event information required to be sent to BMS is noted in an attached 'Bristol-Myers Squibb Early Asset Investigator Sponsored Research (ISR) Import Plan', which describes the method of collection and submission to BMS via the mailbox:

[contact]

When the file is submitted to BMS, it must be noted the file contains

1) all Non Serious Adverse Events (only adverse events not previously submitted to BMS within the 3 months)

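### Does calling the trial single blind, without saying who is blinded, require a change to the plan?

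*Combined protocol and SAP*

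**What the plan says.** The label appears twice. The Protocol Summary gives the methodology as "Randomized, controlled, single blind trial", and Section 4.1 says "The trial is a phase II, randomized controlled, single blinded study evaluating 2 study arms". Neither names the blinded party.

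Other sections bear on who could be blinded:

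- **Infusions (Section 6.1.5).** Nivolumab runs for 30 minutes. For the combination, staff are told to "infuse Nivolumab first followed by a 30 minute period of observation followed by infusion BMS-986253 over 120 minutes on the same day". No placebo or sham infusion is described for Arm 1.
- **Drug supply (Section 6.1.2).** Every vial of both agents is listed as open label.
- **Toxicity table (Section 6.1.7).** The grade 3 diarrhoea or colitis row gives one action for monotherapy, beginning "Withhold dose when single", and a different one for the combination. It is cited here only because it shows that treating staff must know the arm.
- **Randomization (Section 10.6).** Centres receive the assignment from the coordinating centre. Nothing is said about concealing it afterwards.
- **Response assessment.** Section 4.2.1 says "ORR will be determined based upon RECIST v. 1.1 criteria". Section 6.1.8 treats a patient who has reached first imaging as evaluable: "From a statistical standpoint, this will be an evaluable participant for objective response based on RECISTv1.1 criteria". Section 10.4.2 takes the best response over the MRI or CT scans. None of these, nor the visit sections or the schedule of events, names the reader or says whether the reader knows the arm.

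Some relevant material was not available: the figure under "Schematic of Study Design", the Key Roles text that Section 8.5 points to ("See Section 1, Key Roles for contact information"), the consent form, and the core lab instructions listed in Section 19. Section 10.1 says that the formal SAP is to be completed before database lock.

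**The concern.** In its usual sense, single blind means that participants do not know their arm. Here a participant could infer it from the length of the visit and the second bag, so that reading is implausible. Treating staff must know the arm. The masking that would matter most for the primary endpoint is that of the person reading the scans, and no available section provides it.

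ORR depends on judging partial response against stable disease on imaging. Time to response, duration of response and progression-free survival rest on the same reads; overall survival does not. A report that repeated the label without explanation could lead readers to think the ORR comparison was read blind when it was not. With 25 patients per arm, a reader who leaned towards the combination would need few changed calls to move the result across the significance line.

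**Working it through.** **Inputs.** Section 10.5: 25 per arm, control ORR 15%, combination ORR 49%, two-sided Z-test with unpooled variance, significance level 0.05. Section 2.2.2: historical stable disease 42%. Section 6.1.5: infusion times.

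**The plan's own figure.** The standard error is sqrt[(0.15 × 0.85 + 0.49 × 0.51)/25] = sqrt(0.3774/25) = 0.1229. Then 0.34/0.1229 − 1.96 = 0.807, and Phi(0.807) = 79.0%. Exact enumeration of the same test gives 79.1%. The stated 80% is reproduced. Nothing in this calculation depends on blinding.

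**Visit length.** Arm 1: 30 minutes. Arm 2: 30 + 30 + 120 = 180 minutes.

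**How close one call can be.** z = (difference in observed proportions)/sqrt{[a(1−a) + b(1−b)]/25}, where a and b are the observed proportions.

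| Control | Combination | z | p |
|---|---|---|---|
| 4/25 | 9/25 | 0.20/sqrt[(0.1344 + 0.2304)/25] = 1.66 | 0.098 |
| 4/25 | 10/25 | 0.24/sqrt[(0.1344 + 0.2400)/25] = 1.96 | 0.0499 |
| 3/25 | 8/25 | 0.20/sqrt[(0.1056 + 0.2176)/25] = 1.76 | 0.079 |
| 3/25 | 9/25 | 0.24/sqrt[(0.1056 + 0.2304)/25] = 2.07 | 0.038 |

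By exact enumeration with a control ORR of 15%, the chance of ending exactly one Arm 2 response short of significance is 2.8%, 11.1%, 11.0% or 7.2% for a true combination ORR of 15%, 30%, 40% or 49%. This follows from the sample size and would be the same with a masked reader. The 0.0499 also depends on the unpooled variance: with pooled variance, 10/25 against 4/25 gives p = 0.059.

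**What biased reading could do (illustration only).** Assume a true ORR of 15% in both arms and stable disease of 42%, and let a fraction f of stable disease in Arm 2 be called partial response. The apparent Arm 2 ORR is 15% + 42% × f. The upgrade rates are assumptions with no source in the documents.

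| f | Apparent Arm 2 ORR | Rejection rate, Arm 2 only upgraded | Rejection rate, both arms upgraded equally |
|---|---|---|---|
| 0 | 15.0% | 5.5% | 5.5% |
| 10% | 19.2% | 7.5% | 5.8% |
| 20% | 23.4% | 13.0% | 6.3% |
| 30% | 27.6% | 21.6% | 6.5% |

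The 42% is historical, and this trial enrols patients without prior systemic therapy (Section 5.1), so its rate may differ. With stable disease of 30% to 50%, upgrading in Arm 2 only gives 6.6% to 8.3% at f = 10% and 14.0% to 27.6% at f = 30%. Only upgrading that differs between arms matters much, and the documents give no evidence of any.

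**What each possible answer would change.**

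- *The response reader is masked.* The label is true but incomplete, and the analysis is as planned.
- *Another role is masked*, such as a laboratory or the biostatistics group. The label is unusual but not false, and the analysis is as planned.
- *No one is masked.* The accurate description is open label, and the analysis is as planned.

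In all three cases the hypotheses (Section 10.2), the intention-to-treat set (10.3), the test (10.4.2) and the sample size (10.5) stay the same.

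**The case for a change.** The strongest case for a change is that it is cheap and concerns the primary comparison. It would take a phrase in the Protocol Summary, a phrase in Section 4.1 and a sentence in Section 10.4.2, with IRB review under Section 13.2. Even if a masked reader is described in the core lab instructions, Section 19 says that attachments are not part of the protocol and can be changed without amendment, so they are a weak place for a design claim made in Section 4.1.

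Part of this stands. No available section names the blinded party, participant blinding is implausible, and a report should not call the ORR read blind unless it was.

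The rest does not carry. The open-label vials and the arm-specific toxicity row fit single blinding in its usual sense, where staff know the arm, so they do not contradict the label. Nor must the blinded party be the response reader for the label to be true. The places most likely to answer the question, including the consent form, could not be checked. Finally, rewording the label alters no reading. Masking only the remaining reads would be worse than leaving them alone, because best response over repeated scans would then mix two reading conditions.

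**Conclusion.** The label is incomplete, but it is not shown to be wrong, and the gap does not call for a change to the plan. Who read the scans, and whether that person knew the arm, is a matter of fact that the sponsor can establish and that the SAP and the report can state in a sentence. Analysts can be expected to do this, and to describe the ORR as assessed with knowledge of arm if that was so. An open-label randomized phase II trial with ORR as its endpoint is a legitimate design.

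The effect of rewording the label on the test, power, sample size and analysis set is nil. The potential bias from an unmasked reader cannot be sized from the documents; the rejection rates of 7.5% to 21.6% rest entirely on assumed one-sided upgrading of 10% to 30% of stable disease. A masked re-read of all stored scans could address that risk, but it is a sensitivity analysis the sponsor may choose, at the cost of reader time. This conclusion assumes that the report will not present the ORR as read blind without support.
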